#### 7.1.1 Study Day and Visit Window Definitions

## **7.1.1.1** Study Day

The first date on which participant receives study drug (or study treatment – AL002 or placebo) per the records with non-missing dates and non-missing volume administered in the dataset corresponding to the Exposure – IV electronic CRF will be designated as **Study Day 1**. Study days for other visits will be calculated as follows:

- Before Study Day 1: Study Day = date of assessment date of Study Day 1.
- On or after Study Day 1: Study Day = date of assessment date of Study Day 1 + 1.

The **last dose date** of study drug will be the date of last dose collected on the Study Drug Completion electronic CRF or the date of last non-missing study drug administration record collected on the Exposure – IV electronic CRF, whichever occurs later.

Protocol No. AL002-2 Last Revision Date: 12 Aug 2025

## 7.1.1.2 Analysis Visit Window Definitions

Analysis Visit weeks referred to in the SAP are labelled differently than the "nominal" names given in the protocols, at one week less. Thus, nominal Week 25 in the protocol is Analysis Visit Week 24 in the SAP, and nominal Week 49 in the protocol is Analysis Visit Week 48 in the SAP.

## 7.1.1.2.1 Efficacy Data

Efficacy endpoints are scheduled to be performed or collected at nominal visits per protocol: Screening, Week 25, Week 49, Week 73, Week 97, early termination (ET), and EFU (only collected if COA is not performed or collected within 12 weeks since the last COA collection). For the efficacy endpoints, assessments will be allocated to analysis visits using the analysis visit window intervals in which they fall in as specified in Table 7-1.

Efficacy data will be summarized based on the analysis visits (hereinafter may be referred to as "visit"), when applicable.

Table 7-1. Analysis Visit Windows for Efficacy Assessments

Nominal Visit per Protocol	Targeted Day of Nominal Visit (Based on Study Day)	Analysis Visit	Analysis Visit Window (Based on Study Day)
Scree			
Screening	-	Baseline b	~ 1
Treati	nent Phase	Baseline	≤1
Week 1 a	1		
Week 25	169	Week 24	[2, 253]
Week 49	337	Week 48	[254, 421]
Week 73	505	Week 72	[422, 589]
Week 97	673	Week 96	≥ 590

<sup>a COAs are scheduled to be performed/collected prior to dosing.

When assigning an analysis visit, also assign relative time as Predose or Post-infusion, which should correspond to Predose or Post-infusion as specified in Section 7.1.4.3.

Table 7-6. Analysis Visit Windows for Central ECG Assessments

Analysis Visit 	Target Day	Analysis Visit Window (Based on Study Day)
Baseline	-	≤ Day 1 Predose
Day 1 Postdose	1	Day 1 Postdose
Week 24	169	[2, 253]
Week 48	337	≥ 254

When assigning an analysis visit, also assign relative time as Predose or Post-infusion, which should correspond to Predose or Post-infusion as specified in Section 7.1.4.3.

Last Revision Date: 12 Aug 2025

Table 7-7. Analysis Visit Windows for Weight

Analysis Visit	Target Day	Analysis Visit Window (Based on Study Day)
Baseline	-	≤1
Week 4	29	[2, 43]
Week 8	57	[44, 71]
Week 12	85	[72, 99]
Week 16	113	[100, 127]
Week 20	141	[128, 155]
Week 24	169	[156, 183]
Week 28	197	[184, 211]
Week 32	225	[212, 239]
Week 36	253	[240, 267]
Week 40	281	[268, 295]
Week 44	309	[296, 323]
Week 48	337	[324, 351]
Week 52	365	[352, 379]
Week 56	393	[380, 407]
Week 60	421	[408, 435]
Week 64	449	[436, 463]
Week 68	477	[464, 491]
Week 72	505	[492, 519]
Week 76	533	[520, 547]
Week 80	561	[548, 575]
Week 84	589	[576, 603]
Week 88	617	[604, 631]
Week 92	645	[632, 659]
Week 96	673	≥ 660

Protocol No. AL002-2 Last Revision Date: 12 Aug 2025

Table 7-8. Analysis Visit Windows for Vital Signs

Analysis Visit 	Target Day	Analysis Visit Window (Based on Study Day)
Baseline	-	≤ Day 1 Predose
Day 1 Postdose	1	Day 1 Postdose
Week 2	15	[2, 22]
Week 4	29	[23, 36]
Week 6	43	[37, 50]
Week 8	57	[51, 71]
Week 12	85	[72, 99]
Week 16	113	[100, 127]
Week 20	141	[128, 155]
Week 24	169	[156, 183]
Week 28	197	[184, 211]
Week 32	225	[212, 239]
Week 36	253	[240, 267]
Week 40	281	[268, 295]
Week 44	309	[296, 323]
Week 48	337	[324, 351]
Week 52	365	[352, 379]
Week 56	393	[380, 407]
Week 60	421	[408, 435]
Week 64	449	[436, 463]
Week 68	477	[464, 491]
Week 72	505	[492, 519]
Week 76	533	[520, 547]
Week 80	561	[548, 575]
Week 84	589	[576, 603]
Week 88	617	[604, 631]
Week 92	645	[632, 659]
Week 96	673	≥ 660

When assigning an analysis visit window, also assign relative time as Predose or Post-infusion, which should correspond to Predose or Post-infusion specified in Section 7.1.4.3.

Last Revision Date: 12 Aug 2025

Table 7-9. Analysis Visit Windows for MRI Assessments

Analysis Visit	Target Day	Analysis Visit Window (Based on Study Day)
Baseline	-	≤ 1
Week 2	15	[2, 22]
Week 4	29	[23, 36]
Week 6	43	[37, 50]
Week 8	57	[51, 71]
Week 12	85	[72, 127]
Week 24	169	[128, 253]
Week 48	337	[254, 421]
Week 72	505	[422, 589]
Week 96	673	≥ 590

Table 7-10. Analysis Visit Windows for Ophthalmological Examination

Analysis Visit	Target Day	Analysis Visit Window (Based on Study Day)
Baseline	-	≤1
Week 6	43	[2, 78]
Week 16	113	[79, 169]
Week 32	225	[170, 281]
Week 48	337	[282, 421]
Week 72	505	≥ 422

Protocol No. AL002-2 Last Revision Date: 12 Aug 2025

Table 7-11. Analysis Visit Windows for Neurological Examination and Physical Examination

Analysis Visit		Target Day	Analysis Visit Window (Based on Study Day)
	Baseline	-	≤ 1
(Neu	Week 6 rological Examination only)	43	[2, 64]
Week 12	Neurological Examination	85	[65, 141]
Week 12	Physical Examination	83	[2, 141]
Week 28		197	[142, 281]
Week 52		365	[282, 463]
Week 80		561	≥ 464

Table 7-12. Analysis Visit Windows for ADA (Serum) Assessments

Analysis Visit	Target Day	Analysis Visit Window (Based on Study Day)
Baseline	-	≤ 1
Week 2	15	[2, 22]
Week 4	29	[23, 36]
Week 6	43	[37, 50]
Week 8	57	[51, 85]
Week 16	113	[86, 141]
Week 24	169	[142, 211]
Week 36	253	[212, 295]
Week 48	337	[296, 379]
Week 60	421	[380, 463]
Week 72	505	[464, 547]
Week 84	589	[548, 631]
Week 96	673	≥ 632

Protocol No. AL002-2 Last Revision Date: 12 Aug 2025

Table 7-13. Analysis Visit Windows for PK (Serum) Assessments

Analysis Visit	Target Day	Analysis Visit Window (Based on Study Day)
Day 1	1	≤ 1
Week 1	8	[2, 12]
Week 2	15	[13, 22]
Week 4	29	[23, 36]
Week 6	43	[37, 50]
Week 8	57	[51, 71]
Week 12	85	[72, 99]
Week 16	113	[100, 141]
Week 24	169	[142, 211]
Week 36	253	[212, 295]
Week 48	337	[296, 379]
Week 60	421	[380, 463]
Week 72	505	[464, 547]
Week 84	589	[548, 631]
Week 96	673	≥ 632

Table 7-14. Analysis Visit Windows for PK (CSF) Assessments

Analysis Visit	Target Day	Analysis Visit Window (Based on Study Day)
Baseline	1	≤ 1
Week 6	43	[2, 190]
Week 48	337	[191, 421]
Week 72	505	≥ 422

Protocol No. AL002-2 Last Revision Date: 12 Aug 2025

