3.1.5. Efficacy Assessments

A battery of COAs (Appendix 2 [Section 14.2]) will be administered as efficacy assessments over the course of the study, with the primary endpoint being the Clinical Dementia Rating – Sum of Boxes (CDR-SB). Efficacy assessments, including COAs and biomarker assessments, will be made at baseline (screening, Predose Baseline Visit, or on Day 1 prior to dosing), throughout the 48- to 96-week treatment period and, when applicable, at an EFU visit 4 weeks after the last treatment visit. The occurrence of the EFU visit is dependent on the interval of time since the last efficacy assessment during the treatment period; please see sections related to follow-up visits in this protocol and the footnotes to the Schedules of Assessments (Section 14.1) for details. Clinical outcomes and biomarker assessments may or may not occur at an ET visit in the case of early discontinuation; this is also dependent on the interval of time since the last efficacy assessment during the treatment period and is detailed in the footnotes of the Schedules of Assessments (Table 8, Table 9).

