3.1.10. Part 1 Description

Part 1 consists of the first approximately 40 participants who will receive study drug (AL002 or placebo) on Day 1 and Day 29. In Part 1, the administration of the first infusion (Day 1) between any 2 participants at any site will be separated by at least 24 hours. After the Day 43 visit, participants in Part 1 will be treated and followed according to the same dosing and assessment

AL002 Alector, Inc.

schedule outlined for Part 2 for the remainder of their study participation (starting at the Week 9 visit). The iDMC will review all safety data from Part 1 when approximately the 20th participant and approximately the 40th participant (minimum of 32nd) completes their Day 43 visit (see Section 12.1.1). The Part 1 sample size may be increased if there are higher than expected early dropouts (not attributed to safety) to ensure at least 32 participants complete their Day 43 visit.

Part 1 participants will have available safety, tolerability, and PK data at the Day 43 visit, including data from the brain MRI and neurological and ophthalmological examinations reviewed by the iDMC. All participants in Part 1 will receive 2 infusions of study drug (1 infusion on Day 1 and a second infusion on Day 29), and safety and tolerability assessments on Day 8 (±2 days), Day 15 (±2 days), Day 29 (±2 days), and Day 43 (±2 days). On Day 15 and 43, a brain MRI will be performed; participants with MRI evidence of ARIA will not be eligible to receive further administration of study drug. Additionally, on Day 43, an ophthalmological examination, neurological examination, and an LP will be performed.

3.1.11. Definition of a DLAE and the DLAE Assessment Window in Part 1

For Part 1 participants, a DLAE is defined as an AE occurring in the first 43 days that meets any of the following criteria:

- Any SAE that has no other clearly attributable cause beyond study drug, as determined by the Investigator or the Sponsor.
- Any AESI that has no other clearly attributable cause beyond study drug, as determined by the Investigator or the Sponsor.
- Any AE of Grade 3 or higher that has no other clearly attributable cause beyond investigational drug, as determined either by the Investigator or the Sponsor.

If any of the Part 1 participants experiences a DLAE during the DLAE Assessment Window (Day 1 to 43), that participant will discontinue study drug and will be followed for safety until resolution or stabilization of the event.

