6.4. Cerebrospinal Fluid Sampling

For participants who will be tested for evidence of the AD amyloid pathology using the CSF pTau/A β 42 ratio, CSF should be collected via LP at least 5 days prior to randomization. For participants who will be tested for evidence of the AD amyloid pathology using Amyloid PET, and who will also participate in the optional CSF assessments, baseline CSF samples will be collected via LP during the Predose Baseline Visit at least 5 days prior to randomization. LPs should be completed only after the COAs have been administered (eg, CDR). As outlined in Section 6.6.1, COAs should be performed prior to LPs performed on the same day.

For all visits, if an LP and an MRI are performed in the same visit, either (a) the MRI should be performed first or (b) the MRI should be performed at least 3 days after the LP. This minimizes the effect of CSF removal on brain volume measurements. Also, for all visits, if an LP and a PET scan (Amyloid PET or Tau PET) are performed in the same visit, either (a) the LP should be performed first or (b) the LP should be performed at least 12 hours after the PET scan.

Post-baseline CSF samples will be collected as specified in the Schedules of Assessments (Section 14.1) to evaluate PK, PD, and exploratory PD biomarker measures. CSF collection to evaluate PK and PD measures is mandatory for Part 1 participants for all visits through study completion, and optional for Part 2 participants.

Participants will be required to stay in the clinic or hospital for a minimum of 30 minutes after the LP for SFU. Any treated participant who discontinues prematurely should have CSF drawn, unless CSF has been drawn within 12 weeks of discontinuation. Please refer to Section 6.3 for information regarding sample collection.

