Study Period	Screening (Days -78 to -23) ^{ss}	Predose Baseline (Days -22 to -1)											Т	`reat	ment													Follow-ı	пр
Study Week ^a			1 (D1)	3 (D15)	5 (D29)	9 (D57)	13	17	21	25	29	33	37	41	45	49	53	57	61	69 and 69	73	77	81	85	89 and 93	76	EFU/4 weeks ^{qq}	SFU/8 weeks ^d	ETc
Visit Window ⁰⁰			p ⊊∓	p \$ =	p ⊊∓	p 2∓	p ⊊∓	p \$ =	p ⊊∓	p ⊊∓	p ⊊∓	±5d	±5d	±5d	p\$∓	p ⊊∓	p ⊊∓	p⊊∓	+ 5d	±5d									
		Part 2	2 onl	ly									For	parti	cipaı	ıts ra	ındo	mize	d un	ler P	arts	1 an	nd 2						
Amyloid PET ^{dd,ll,mm}	х																												
LP for CSF pTau/Aβ42 ^{ff,ll}	х																												
LP for CSF (mandatory for Part 1; optional for Part 2 participants) ^{ff,ll,mm}		x ^{gg}														x					x						x ^{ee}		x ^{ee}
Tau PET (optional)k,hh,ll		х														х					х						x ⁱⁱ		x ⁱⁱ
Longitudinal Amyloid PET (optional) ^{k,ll,mm}	x	х														х											x ⁱⁱ		x ⁱⁱ
WLSA ^{jj,aa} (optional)		Х			х	X	X	X	х	X	х	X	X	X	X	X	X	X	X	X	X	X	X	X	X	х	\mathbf{x}^1		\mathbf{x}^1

Aβ=amyloid beta; AB42=amyloid beta 1-42; ADA=anti-drug antibody (-ies); ADAS-Cog13=Alzheimer's Disease Assessment Scale-Cognitive Subscale; ADCOMS=Alzheimer's Disease Composite Score; ADCS ADL-MCI=Alzheimer's Disease Cooperative Study-Activities of Daily Living – Mild Cognitive Impairment Scale; AE=adverse event; AESI=adverse event of special interest; APOE e4=apolipoprotein E epsilon4; BP=blood pressure; C-SSRS=Columbia-Suicide Severity Rating Scale; CD33=sialic acid-binding Ig-like lectin 3; CDR=Clinical Dementia Rating; COA=clinical outcome assessments; CSF=cerebrospinal fluid; d or D=day; ECG=electrocardiogram; ET=early termination; EFU=efficacy follow-up; FU=follow-up; Ig=immunoglobulin; LP=lumbar puncture; MMSE=Mini-Mental State Examination; MRI=magnetic resonance imaging; mRNA=messenger RNA; PD=pharmacodynamic(s); PE=physical examination; PET=positron emission tomography; PK=pharmacokinetic(s); pTau=phosphorylated tau; RBANS-Update=Repeatable Battery for the Assessment of Neuropsychological Status-Update; RDVF=Research Diagnostic Verification Form; SAE=serious adverse event; SFU=safety follow-up; TMEM106b=transmembrane protein 106b; TPTD=treatment period termination date; TREM2=triggering receptor expressed on myeloid cells 2; WGS=whole genome sequencing; WLSA=Winterlight Labs Speech Assessment; WOCBP=woman of childbearing potential.

a Study Day number and Study Week number begin with 1 on the day of the first administration of study drug.

AL002 Alector, Inc.

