- dd Screening for amyloid positivity. Positivity on either Amyloid PET or CSF pTau/Aβ42 is sufficient. Confirmation of COA scores for eligibility must be received prior to performing Amyloid PET scans.
- ce If CSF has been drawn within 12 weeks, it should not be drawn at this visit. This applied to the EFU or ET visits. Participants who discontinue due to ARIA may be requested to have an LP per Investigator discretion. LP should be performed at the SFU visit if needed.
- IP should not be performed on the same day when COAs are performed. Participants will be required to stay in the clinic or hospital for a minimum of 30 minutes after the procedure for SFU. LPs performed during screening will be performed at least 5 days prior to the expected D1 dosing visit or randomization (whichever is sooner). LP should not be performed unless results from coagulation laboratory assessments were within clinically acceptable limits within 4 weeks±5 days.
- Part 2 participants who do not receive a LP during the screening period for eligibility, but agree to participate in the optional CSF sampling, a Predose Baseline Visit will occur to schedule and perform an LP prior to Day -5. Confirmation of COA scores for eligibility must be received prior to performing the LP.
- hh For participants in countries where local regulations allow, baseline (optional) Tau PET imaging should be performed prior to first dosing with study drug only after a participant has demonstrated eligibility for study participation, based on completion of all other screening assessments. In some cases, the initial (baseline) Tau PET scan may be performed after study drug has commenced. Sponsor agreement will be needed for baseline Tau PET scans occurring after dosing has commenced. Participants who receive an optional Tau PET scan at baseline will receive 1 or more repeated scans after beginning study drug.
- ii If Tau PET has been performed within 24 weeks, it should not be repeated at this visit. If Amyloid PET has been performed within 24 weeks, it should not be repeated at this visit. This applies to both the EFU and ET visits.

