## 7.1.1.2.3 Fluid (Plasma, CSF) and PET Imaging (Amyloid and Tau) Biomarker Data

Analysis visit windows for the biomarker parameters are defined in a similar manner as those for the efficacy parameters. Biomarker data will be allocated to analysis visits corresponding to the analysis visit window intervals in which they fall in as specified in Table 7-15 to Table 7-19.

Table 7-15. Analysis Visit Windows for PD Plasma Biomarker Assessments

Analysis Visit	Target Day	Analysis Visit Window (Based on Study Day)
Baseline	1	≤ 1
Week 1	8	[2, 12]
Week 2	15	[13, 22]
Week 4	29	[23, 36]
Week 6	43	[37, 50]
Week 8	57	[51, 71]
Week 12	85	[72, 99]
Week 16	113	[100, 141]
Week 24	169	[142, 211]
Week 36	253	[212, 295]
Week 48	337	[296, 379]
Week 60	421	[380, 463]
Week 72	505	[464, 547]
Week 84	589	[548, 631]
Week 96	673	≥ 632

Table 7-16. Analysis Visit Windows for CSF Biomarker Assessments

Analysis Visit	Target Day	Analysis Visit Window (Based on Study Day)
Baseline	1	≤ 1
Week 6	43	[2, 190]
Week 48	337	[191, 421]
Week 72	505	[422, 589]
Week 96	673	≥ 590

Protocol No. AL002-2 Last Revision Date: 12 Aug 2025

Table 7-17. Analysis Visit Windows for Amyloid PET Assessments

Analysis Visit	Target Day	Analysis Visit Window (Based on Study Day)
Baseline	1	≤ 1
Week 48	337	[2, 505]
Week 96	673	≥ 506

Table 7-18. Analysis Visit Windows for Tau PET Assessments, True Baseline\*

Analysis Visit	Target Day	Analysis Visit Window (Based on Study Day)
Baseline	1	≤ 1
Week 48	337	[2, 421]
Week 72	505	[422, 589]
Week 96	673	≥ 590

\*True baseline: baseline corresponds to the pre-dose visit (prior to dosing).

Table 7-19. Analysis Visit Windows for Tau PET Assessments, Redefined Baseline (Sensitivity Analysis)\*

Analysis Visit	Target Day	Analysis Visit Window (Based on Study Day)
Baseline_R	1	≤ Day 1 Predose, if it exists. If not, then day of Week_R 48 nonmissing result (up to Day 421)
Week_R 48	337	[2, 421]
Week_R 72	505	[422, 589]
Week_R 96	673	≥ 590

\*Redefined baseline: baseline corresponds to either the pre-dose visit (prior to dosing) if the pre-dose Tau PET scan is evaluable, or 1st postdose visit if the pre-dose Tau PET scan is missing.

Protocol No. AL002-2 Last Revision Date: 12 Aug 2025

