#### 7.6 Pharmacokinetic Endpoints

All PK summaries will be performed on the PK Set. AL002 concentration will be summarized by analysis visit (refer to Table 7-13 and Table 7-14 for analysis visit window definition) and nominal time point as collected, separately for serum and CSF PK. Summary statistics will include coefficient of variation (CV) as percent and geometric mean in addition to the descriptive statistics (excluding Q1 and Q3) described in Section 7.1.

AL002 mean (+ SD) concentration-time data will be plotted (linear and semi-log) by elapsed time since the first study drug administration (in hours, i.e., (time of collection – time of the first study drug administration + 1) and treatment group for the first dose, separately for serum and CSF PK. The same plot (linear and semi-log) will be repeated for the seventh dose.

AL002 mean (+ SD) trough concentration-time data will also be plotted (linear) by elapsed time since the first study drug administration (in nominal weeks) by ADA group (positive and negative), separately for serum and CSF PK. In each ADA group, all treatment groups will be combined. The ADA positive group includes all participants who had at least one positive ADA result any time post-baseline. The ADA negative group includes all participants whose ADA results were all negative post-baseline. Participants who did not have any ADA post-baseline result will be excluded from this plot.

For the summaries and mean plots of AL002 concentrations, concentrations that are below LLOQ (below the limit of quantifications (BLQs)) before the first measurable concentrations on Study Day 1 will be set to zero, and all BLQs after Study Day 1 will be set to missing. The rules specified in Section 7.1.4.1.1 do not apply to PK.

Potential correlations of serum and/or CSF PK data with demographics, safety (including QT changes), efficacy, and PD measures may be explored, as data allow. Additional modeling, including population PK analysis and/or PK/PD analyses to characterize these correlations may be performed. These additional analyses of PK/PD data will be covered in a separate analysis plan and reported separately from the CSR.

The AL002 concentration data will be listed for the ATS.

Protocol No. AL002-2 Last Revision Date: 12 Aug 2025

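### The CSF PK windows omit the Week 96 row that the CSF biomarker table has, so late follow-up CSF gets two visit labels; the CSF plots for doses 1 and 7 have no scheduled post-dose samples

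*SAP*

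**What the plan says.** **Windows.** "Table 7-14. Analysis Visit Windows for PK (CSF) Assessments" (SAP 7.1.1.2.2) has Baseline, Week 6 [2, 190], Week 48 [191, 421] and Week 72 from Day 422 onward. "Table 7-16. Analysis Visit Windows for CSF Biomarker Assessments" (SAP 7.1.1.2.3) has the same first three rows, then Week 72 [422, 589] and Week 96 from Day 590. For PK, Section 7.1.1.2.2 also limits post-baseline windows to 90 days after the last dose; later samples are only listed.

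**When CSF is drawn.** Protocol Section 6.4 says: "Post-baseline CSF samples will be collected as specified in the Schedules of Assessments". In Part 1, Section 3.1.10 adds an early LP: "Additionally, on Day 43, an ophthalmological examination, neurological examination, and an LP will be performed". In Table 9 of Section 14.1, the row "LP for CSF (mandatory for Part 1; optional for Part 2 participants" marks Predose Baseline, Week 49, Week 73, EFU and early termination (ET). For EFU and ET, a Table 9 footnote states: "If CSF has been drawn within 12 weeks, it should not be drawn at this visit". Section 3.1.5 places the final efficacy assessment "at an EFU visit 4 weeks after the last treatment visit".

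**Outputs.** SAP Section 7.6 summarizes concentrations by analysis visit and collected nominal time point, with serum and CSF kept apart. It also asks for mean concentration-time plots by elapsed time "and treatment group for the first dose, separately for serum and CSF PK", and for the same plots at the seventh dose.

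**The concern.** One LP supplies both the PK and the biomarker sample, yet the two tables label it differently once it falls on Day 590 or later. The PK table then places a late follow-up sample in the same window as the Week 73 sample. SAP Section 7.1.3 says how to choose among several records for efficacy, safety and PD biomarker data, but not for PK. The programmer would have to decide alone whether both values enter the Week 72 CSF summary.

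The plots raise a separate problem. A concentration-time curve after a given dose needs samples between that dose and the next, and the LP schedule does not appear to supply any for doses 1 and 7.

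CSF AL002 concentration is a named PK objective. At stake is whether its descriptive displays show what their labels say.

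**Working it through.** **Inputs.** Study day of protocol week w = 7(w − 1) + 1. Fixed post-dose LPs are Day 43 (Part 1), Week 49 (Day 337) and Week 73 (Day 505). EFU is 28 days after the final treatment visit. An EFU LP is due if more than 84 days (12 weeks) have passed since the last LP (Protocol 3.3.4). Doses are every 28 days from Day 1.

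**Reproducing the cut-points.** They are midpoints between adjacent target days:
- (43 + 337)/2 = 190, so 190/191, in both tables.
- (337 + 505)/2 = 421, so 421/422, in both tables.
- (505 + 673)/2 = 589, so 589/590, in Table 7-16 only.

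**Where EFU LPs fall.** On-schedule visits are assumed. The last LP is Day 337 for final weeks before 73, and Day 505 from Week 73.

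| Final week | EFU day | Days since last LP | LP due | Table 7-14 | Table 7-16 |
|---|---|---|---|---|---|
| 49, 53, 57 | 365, 393, 421 | 28, 56, 84 | no | – | – |
| 61, 65, 69 | 449, 477, 505 | 112, 140, 168 | yes | Week 72 | Week 72 |
| 73, 77, 81 | 533, 561, 589 | 28, 56, 84 | no | – | – |
| 85 | 617 | 112 | yes | Week 72 | Week 96 |
| 89 | 645 | 140 | yes | Week 72 | Week 96 |
| 93 | 673 | 168 | yes | Week 72 | Week 96 |
| 97 | 701 | 196 | yes | Week 72 | Week 96 |

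The last four rows are the conflict. These samples lie 617 − 505 = 112 days (16 weeks) to 701 − 505 = 196 days (28 weeks) after the PK target day. A participant in these rows who had the Week 73 LP has two samples in the PK Week 72 window.

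**The 90-day cap.** A participant dosed at the final treatment visit is 28 days past the last dose at EFU, so the sample stays in the summary. The sample drops out only if the last dose was more than 90 − 28 = 62 days before the final treatment visit.

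**Dose intervals.** Dose 1 covers Day 1 to Day 29. Dose 7 is on Day 1 + 6 × 28 = 169, and its interval ends on Day 197. The fixed LPs relate to dosing as follows:
- Day 43 is 14 days after dose 2 (Day 29).
- Day 337 is 28 days after dose 12 (Day 309).
- Day 505 is 28 days after dose 18 (Day 477).

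Scheduled post-dose LPs in the dose 1 interval: 0. In the dose 7 interval: 0.

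**The case against.** Several objections have force.

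- **Table 7-14 follows the fixed LP visits.** Weeks 6, 48 and 72 are the Day 43, Week 49 and Week 73 LPs, and no Week 97 LP exists. A reader might infer that the table contradicts the LP schedule; it does not. Leaving the last window open is also common in this SAP (Tables 7-4, 7-10 and 7-11). However, those are safety tables, and Section 7.1.3.2 gives safety data a closest-to-target rule. Tau PET has the same pattern of fixed visits plus EFU/ET, and Table 7-18 gives it a Week 96 row from Day 590. Section 7.7.1.1 expects some CSF data at Week 96 and describes that sample as limited.
- **Few participants are affected.** LPs are optional in Part 2 (about 288 of 328 participants), extension-study entrants have no EFU, and the 90-day cap removes those who stopped drug well before. It would be wrong to read this as every late EFU sample being mislabelled. The documents give no count.
- **Double counting is possible, not certain.** The nominal time point used in Section 7.6 might separate the EFU sample from the Week 73 sample, but the SAP does not say so.
- **Pooling may matter little pharmacologically.** For participants still dosed, both samples are taken about 28 days after a dose, and the serum half-life is about 9 days (Protocol 1.4). This limits the harm but does not make the label correct.
- **PK and biomarker data can still be linked.** A reader might infer that results from one LP cannot be matched. They can, by participant and date, and PK/PD modelling is in a separate plan.
- **The plots need not be blank.** A pre-dose value exists, and an LP after ARIA or an ET LP could add isolated points. These would not make a profile. Section 7.6 already plans a CSF trough plot by ADA group, but it combines the dose groups.

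**Conclusion.** The point holds within narrow limits. For participants who have LPs (Part 1, or Part 2 by consent), do not enter the extension study, finish at Weeks 85 to 97 and are within 90 days of their last dose, the EFU CSF sample on about Days 617 to 701 is Week 72 for PK and Week 96 for biomarkers. The same person's Week 73 sample can share that PK window, with no stated rule for choosing between them. Separately, the CSF plots for doses 1 and 7 cannot show a concentration profile from scheduled samples.

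The effect is confined to descriptive CSF PK tables and figures. No efficacy estimate, test or safety decision changes. The day figures assume on-schedule visits and a completed Week 73 LP; visit windows of ±5 days would move them slightly. The number affected cannot be derived from the documents.

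**What to change.** Three edits to the SAP:

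1. Give Table 7-14 the Table 7-16 windows: Week 72 [422, 589] and Week 96 from Day 590, still subject to the 90-day limit for PK.
2. State that one CSF PK sample per participant per window is summarized, namely the one closest to the target day.
3. In Section 7.6, remove CSF from the first-dose and seventh-dose plots. Show CSF concentration by analysis visit (Weeks 6, 48, 72 and 96) and treatment group instead.

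A CSF-to-serum ratio should not be added to that display, because Protocol Table 9 schedules no serum PK sample at EFU.

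The cost is a revised table, one sentence and a change to two plot specifications. No new data and no protocol amendment are needed.
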